**Study Sponsor**

[name] PhD

Principal Investigator

Massachusetts General Hospital

[name]

The method and general statistical analytical procedure of study, sequential parallel comparison design, has been described in previously published materials. That being that subjects are allocated to receive either the active treatment or placebo in both phases, or receive placebo within the first phase then receive the active treatment in the second. Therefore, there will be three groups analyzed: Active-Active, Sham-Sham, and Sham-Active. Only those considered non-responders in the first phase are analyzed within the second phase, as it is hypothesized they have a reduced placebo response, or have not found the initial phase of the intervention effective (Fava et al. 2003).

Process of calculation has been described in the Statistical appendix of the reference above. That being:

"Assume that patients will be randomized into three groups, the first two groups will initially receive placebo, those patients that do not respond to placebo will receive placebo (group 1) or drug (group 2). The third group will initially receive drug. The proportions randomized to the three groups will be  $a$ ,  $a$  and  $1 - 2a$ .

Let  $p_1$ ,  $q_1$  be the response rates to the first administration of drug and placebo respectively and let  $p_2$ ,  $q_2$  by the responses to the second treatment. To analyze these data we use a statistic based on  $h = w(p_1 - q_1) + (1 - w)(p_2 - q_2)$ . The weight,  $w$  and the randomization fraction,  $a$  are chosen to maximize the power of the test, based on the alternative hypothesis.

The standard error for  $h$  requires a special formula because some of the same patients who are included in the estimation of  $p_2$ ,  $q_2$  are included in the estimation of  $p_1$ ,  $q_1$ . The delta method was used to compute the standard error of  $h$ ...

Then

$$h = w \left( \frac{n_{3,1}}{n(1 - 2a)} - \frac{(n_{1,3} + n_{2,3})}{2na} \right) + (1 - w) \left( \frac{n_{2,1}}{n_{2,1} + n_{2,2}} - \frac{n_{1,1}}{n_{1,1} + n_{1,2}} \right)$$

where  $n$  is the total number of patients. Let  $D$  be the column vector of derivatives of  $h$  with respect to  $n_{3,1}$ ,  $n_{1,3}$ ,  $n_{2,3}$ ,  $n_{2,1}$ ,  $n_{2,2}$ ,  $n_{1,1}$ ,  $n_{1,2}$ , and let  $V$  be the variance covariance matrix of  $n_{3,1}$ ,  $n_{1,3}$ ,  $n_{2,3}$ ,  $n_{2,1}$ ,  $n_{2,2}$ ,  $n_{1,1}$ ,  $n_{1,2}$ , from the multinomial distribution. Then the standard error of  $h$  is given by  $\sqrt{D}VD$ , which is computed with the observed values of  $p_1$ ,  $p_2$ ,  $q_1$ ,  $q_2$ . The formula below is a simplified calculation of the standard error of  $h$  derived using Mathematica (Wolfram Research).

$$\sqrt{\frac{-2(-1 + 2a)p_2(-1 + w)^2 + 2(-1 + 2a)p_2^2(-1 + w)^2 - 2(-1 + 2a)q_2(-1 + w)^2 + 2(-1 + 2a)q_2^2(-1 + w)^2 + (-1 + q_1)((-1 + q_1)q_1 + 2a(-p_1 + p_1^2 + q_1 - q_1^2))w^2}{2a(-1 + 2a)(-1 + q_1)}}$$

To test the null hypothesis, we use  $z = h/s$ . The values of  $a$  and  $w$  were calculated by substituting the alternative hypothetical values of  $p_1$ ,  $p_2$ ,  $q_1$ ,  $q_2$  and finding the values of  $a$  and  $w$  that maximize  $z$ . The power of the test is then  $\sum(z - 1.96)$ , where  $\sum$  is the cumulative distribution of

the normal distribution. Software for computing  $a$ ,  $w$  and calculating the power of the test is available from the authors. "

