### 5.3 Sample Size

With respect to the TLT study, we expect 100 subjects to sign informed consent, including screen failures. Assuming that 1/2 will screen fail this will lead to randomization of 50 subjects. In PART-1 (CW), we will have a n=24 with a 1st randomization 2:1 (sham:NIR), which will result in 16 subjects receiving sham and 8 subjects receiving NIR. We then assume 70% non-response to sham which leads to 11 sham subjects who are non-responders and who will undergo the 2nd randomization (week 6). Assuming a dropout rate of 24% before week 6, we anticipate that 9 subjects from the sham group will be eligible for the 2nd randomization 1:1 (sham:NIR). This 2nd randomization (week 6) will result in approximately 5 subjects receiving sham and 4 subjects receiving NIR. According to the Sequence Parallel Comparison (SPD) design the data from the 1st randomization (week 0 to 6 of the trial) and the data from the 2nd randomization (week 6 to 12 of the trial) can be pooled resulting in a total of 16+5=21 available sham subjects and 8+4=12 available NIR subjects. With this sample we have estimated >80% power to detect a significant difference ( $p \leq 0.05$ ) in depression outcome based

on the antidepressant effect size detected in our prior MGH study (ELATED-2). In PART-2 (PW) we will have an even larger power to detect a significant difference since our sample of subjects at the 1st randomization will be larger (n=26).

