### **Primary Analysis**

QIDS: The changes in QIDS scores and the response rates, which was defined as 50% or more drop in QIDS score, are the two main output measures of the current study. All statistical analyses are performed on R software version 3.6.2 (R Core Team, 2019) with SPCDAnalyze package version 0.1.0 (Schoenfeld 2019). The package uses constrained longitudinal data analysis model. The level of statistical significance was set at  $p \leq 0.05$ .

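### The only response-rate test the SAP writes out, z = h/s, has a two-sided type I error of about 8–13% at the planned PART-1 sizes, and the SAP does not say whether this is the test that will be used

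*SAP*

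**What the plan says.** The opening part of the SAP adopts a published appendix as its method: "Process of calculation has been described in the Statistical appendix of the reference above". The quoted text defines h as a weighted sum of the phase-1 and phase-2 differences in response rate. It obtains s by the delta method, "which is computed with the observed values of" the four rates, and then continues "To test the null hypothesis, we use" z = h/s. The power expression uses 1.96, so a two-sided 5% test against the normal distribution is implied. No exact, pooled-variance or small-sample alternative is given.

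The SAP's Primary Analysis section says that QIDS change and "the response rates, which was defined as 50% or more drop in QIDS score, are the two main output measures". It also says that all analyses are run in the SPCDAnalyze package and that "The package uses constrained longitudinal data analysis model". "The level of statistical significance was set at" p ≤ 0.05. The Secondary Analysis section repeats this for HAM-D.

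Protocol section 5.3 gives the PART-1 sizes: 16 sham and 8 active in phase 1, then a second randomisation that "will result in approximately 5 subjects receiving sham and 4 subjects receiving NIR". Protocol section 5.6 weights the two phases equally.

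**The concern.** The normal reference for h/s relies on each arm being large enough for its estimated variance to be stable. With four or five subjects in an arm, 0% or 100% responders is a common result. Such an arm adds nothing to the plug-in variance, so s is too small and z too large. If this is the test applied, a main outcome is declared significant under the null more often than the stated 5%.

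The SAP also leaves the reader unsure which test applies. Its opening text describes one for proportions. Its Primary Analysis section names a model without saying how that model handles a binary response.

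**Working it through.** **Inputs.** Phase 1 has 8 active and 16 sham; phase 2 has about 4 active and 5 sham (protocol 5.3). Phase-1 null rate is 0.30, from the assumed 70% sham non-response (5.3). Attrition follows "Assuming a dropout rate of 24% before week 6" (5.3). Phase weight is w = 0.5 (5.6). The critical value is 1.96 (SAP). The phase-2 null rate is not in the documents, so 0.1 to 0.3 is assumed, with 0.4 as an extension.

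**The plan's subject flow.** 24 × 2/3 = 16 sham and 24 × 1/3 = 8 active. 16 × 0.70 = 11.2, stated as 11. 11 × 0.76 = 8.4, stated as 9 and split 5 and 4. The flow reproduces to within rounding.

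**Statistic.**

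h = w(p1 − q1) + (1 − w)(p2 − q2)

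s² = w²[p1(1 − p1)/8 + q1(1 − q1)/16] + (1 − w)²[p2(1 − p2)/4 + q2(1 − q2)/5]

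This is the delta-method variance on its proper scale. The closed form printed in the SAP lacks a division by n. That is a separate matter, and the result here does not depend on it.

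**Mechanism.** With a true phase-2 rate of 0.2:

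- The arm of 4 is at 0% or 100% with probability 0.8⁴ + 0.2⁴ = 0.411.
- The arm of 5 is at 0% or 100% with probability 0.8⁵ + 0.2⁵ = 0.328.
- At least one arm is, with probability 1 − 0.589 × 0.672 = 0.60. When the sizes vary with 24% loss, simulation gives 65%.

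**One possible data set.** Phase 1: 0/8 active, 5/16 sham. Phase 2: 0/4 active, 1/5 sham.

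- h = 0.5(0 − 0.3125) + 0.5(0 − 0.2) = −0.256.
- Plug-in: s² = 0.25 × (0 + 0.01343 + 0 + 0.03200) = 0.01136, s = 0.107, z = −2.40.
- Arms pooled within phase (null rates 5/24 and 1/9): s² = 0.25 × (0.03092 + 0.04444) = 0.01884, s = 0.137, z = −1.87.

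The plug-in version rejects and the pooled-variance version does not. The false rejection here goes against TLT.

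**Two-sided type I error, exact enumeration at 8/16 and 4/5, phase-1 null rate 0.3.**

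| Phase-2 null rate | Plug-in s |
|---|---|
| 0.1 | 8.2% |
| 0.2 | 9.2% |
| 0.3 | 10.0% |
| 0.4 | 10.5% |

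With a pooled null variance at the same sizes and rates the error is 5.1–5.9%, which identifies the plug-in s as the cause. Keeping the plug-in s would need a critical value of about 2.5–2.6.

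**Simulation of the sequential flow** (phase-1 rate 0.3, phase-2 rate 0.1/0.2/0.3).

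- PART-1, no attrition: 8.1/8.9/9.5%.
- PART-1, 24% loss: about 9–13%, depending on the phase-2 rate and on whether dropouts stay in the phase-1 denominators.
- PART-2 (n = 26): 7.9–9.1% without attrition, 8.7–12.1% with 24% loss.
- Both Parts together (n = 50): about 6–8%.

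**Direction, PART-1.** Rejections favouring TLT, against a nominal 2.5%:

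- No attrition: 3.0/3.8/4.3%.
- 24% loss, observed denominators: 3.9/4.8/5.5%.
- 24% loss, denominators as randomised (the form in which the SAP writes h): 3.1/4.6/5.9%.

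**Sensitivity.** For w from 0.3 to 0.8 the two-sided error is 7.0–11.8%. With very low null rates (0.1 in phase 1, 0.02–0.05 in phase 2) it falls to about 4%.

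**The case against.** The strongest objection is that z = h/s may not be the test used. The passage containing it is a block quotation that includes design-stage material, such as choosing a and w and computing power. The trial's own statement is in Primary Analysis, where every analysis goes to a package with a constrained longitudinal model. This stands in part. A reader might infer that the SAP definitely tests response with z = h/s, but the documents do not settle it. They also give no other test for a response rate, so the error rate of the one that is written out matters until the SAP says otherwise.

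A second objection concerns the consequence. A reader might infer that an ineffective Part would be declared positive about twice as often as claimed. The figures do not support that in most scenarios. Without attrition most of the excess consists of rejections in favour of sham, because the small active arm often has no responders. Error favouring TLT reaches about double only with attrition and a phase-2 rate of roughly 0.2 or more.

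Third, the range rests on assumptions. The phase-2 null rate is assumed, and the SAP itself expects a reduced placebo response among non-responders, which makes the upper end less likely. The SAP's quoted text chooses w to maximise power and gives no value, so 0.5 comes from the protocol. The SAP also does not say whether the Parts are analysed separately, although protocol section 5.2 wants the two effect sizes estimated separately. These points move the size of the excess. They remove it only at very low null rates, well below the 30% phase-1 sham response that the plan assumes.

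Finally, the protocol calls this a feasibility study, and the change scores are untouched. Both are true, and they limit the reach of the point.

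**Conclusion.** The point holds conditionally. If response is tested by z = h/s with plug-in variances, a PART-1 analysis at the planned sizes has a two-sided type I error of about 8–10% without attrition and about 9–13% with 24% loss, not 5%. PART-2 is similar, and combining the Parts leaves about 6–8%. Error favouring TLT is about 3–6% against 2.5%. These figures assume w = 0.5, a phase-1 null rate of 0.3 and a phase-2 null rate of 0.1–0.3.

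The finding covers QIDS and HAM-D response only. It should not be read as showing inflated error for QIDS or HAM-D change. Whichever test was intended, the opening text and the Primary Analysis section need to be reconciled.

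**What to change.** State in the Primary and Secondary Analysis sections which test is applied to QIDS and HAM-D response, how it relates to the quoted z = h/s and to the package model, which w is used, and whether the Parts are analysed separately. Keep h as the estimate.

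Replace the plug-in z-test with one of these:

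- **Preferred: a re-randomisation test that reproduces the actual allocation.** Re-draw the initial 1:2 allocation by Part and block, then the 1:1 allocation at week 6 among sham subjects still in the study, and recompute h each time. A single re-draw of three fixed sequences would not match the protocol, because the second allocation happens at week 6 and early dropouts never receive it. An exact test of this type, conditional on the phase totals at 8/16 and 4/5, had an error of 2.3–3.8%.
- **Minimum: a pooled null variance in s.** This brings the error to about 5–6% but does not guarantee 5%.

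The cost is SAP wording, a short program and fewer nominally significant results. In one scenario (response 0.6 vs 0.3 in phase 1 and 0.5 vs 0.2 in phase 2), rejection fell from 47% with the plug-in z-test to 27% with a simpler one-stage re-randomisation test. Part of that 47% comes from the inflated error, so the drop is not all lost power. The two-stage version would need its own power check.

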### **Primary Analysis**

QIDS: The changes in QIDS scores and the response rates, which was defined as 50% or more drop in QIDS score, are the two main output measures of the current study. All statistical analyses are performed on R software version 3.6.2 (R Core Team, 2019) with SPCDAnalyze package version 0.1.0 (Schoenfeld 2019). The package uses constrained longitudinal data analysis model. The level of statistical significance was set at  $p \leq 0.05$ .

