**Endpoints:**

**Safety** - The safety endpoints will evaluate the TLT and sham groups for differences in tolerability through 12 weeks of follow-up.

**Efficacy** - The efficacy endpoint will be the antidepressant effect of TLT through week 12, as assessed using the QIDS-C scale.

**Engagement of Neuro-Inflammation** – The effect of TLT on inflammation will be assessed at week 6 and 12 by measuring the plasma levels of IL6, TNF- $\alpha$ , IL-1 $\beta$  as primary cytokines (compared to baseline).

**Engagement of Cognitive circuitry** – The effect of TLT on cognition will be assessed at week 6 and 12 by measuring pattern recognition and cognition with emotional stimuli (compared to baseline).

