### 5.2 Specific Aims

A. To assess the antidepressant effect of the Transcranial continuous or pulse Light Therapy in depressed subjects.

Hypothesis 1: We anticipate that TLT will decrease QIDS-C and HAM-D 17 total scores in study subjects significantly more than the Sham treatment. We expect that we will be also able to estimate the effect size of the antidepressant action of Transcranial continuous and pulse Light Therapy, separately.

B. To assess the safety and tolerability of the Transcranial continuous / pulse Therapy in depressed subjects

Hypothesis 2: We predict that the Transcranial continuous and pulse Light Therapy will be safe and well-tolerated by depressed patients, as assessed by the following rating scales: SAFTEE-SI and ADVERSE EVENTS FORM. We anticipate differences in between TLT and Sham treatment as concerns side-effects.

Secondary Aims include the assessment of neuro-inflammation and cognitive circuitry. We predict that TLT decreases plasma levels of IL6, IL8, TNF- $\alpha$ , IL-1 $\beta$  more than sham. TLT will also improve attention, inhibition and executive functions more than sham.

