#### **5.6 *Efficacy Analyses for Primary Aims***

The study (both PART-1 continuous and PART-2 pulse) will utilize a 2-phase sequential parallel design with 6 weeks treatment duration in each phase. Eligible patients will be randomized to two groups with a 1:2 ratio, to ensure adequate sample in phase 2 (week 6-12). Patients in the first group (TLT) will receive TLT (continuous in PART-1 and pulse in PART-2) at both phases (week 0-12). Patients in the second group (Sham) will receive sham at phase-1 and will undergo a 1:1 ratio randomization to either TLT or sham in phase-2 (week 6-12), respectively. Patient retention rates during phase-1 of the trial are assumed to be 76%, based on our earlier study ELATED-2. The treatment differences from phase-1 and phase-2 will be combined with equal weights to estimate the overall treatment effect.

For the primary efficacy analysis, all patients in phase 1 will be compared, together with sham non-responders from phase 2 (sham non-responders are defined as those patients who failed to achieve a 50% decrease in their QIDS-C score at visit 13).

A. Antidepressant effect of the TLT: To test the significance of the antidepressant effect of TLT (in both PART-1 and PART-2) we will use a T-test for mean differences of two related measures and will primarily look at QIDS-C and HAM-D 17 total score mean change on TLT and compare it with the QIDS-C and HAM-D 17 total score mean change on Sham, the significance will be set at a p-value  $\leq 0.05$ . The time-points to estimate the mean differences are baseline and week 6 for all subjects and for subjects non-responders to sham who are re-randomized also week 6 and week 12. Rates of responders according to the CGI-Improvement (score 1 or 2) will be estimated at week 6 and 12 of the study (no statistics planned). Both completer analysis and intent-to-treat analysis will be performed to analyze the severity of depression at endpoint. Patient attrition and dropouts

will be analyzed. Potential differences between treatment groups in dropouts will be examined with the Fisher's Exact test.

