### **Secondary Analysis:**

HAMD: Secondary outcome measure was change in HAM-D scores and response rate defined as 50% or more drop in HAMD score. All statistical analyses performed R software version 3.6.2 (R Core Team, 2019) with SPCDAnalyze package version 0.1.0 (Schoenfeld 2019). The package uses constrained longitudinal data analysis model. The level of statistical significance was set at  $p \leq 0.05$ .

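### The SAP names two main QIDS outcomes at one unadjusted 0.05 with no rule for success, and the protocol's primary-aim analysis names a different pair

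*SAP*

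**What the plan says.** **SAP, Primary Analysis.** QIDS change and QIDS response, defined as a drop of 50% or more, "are the two main output measures of the current study". One significance level, p≤0.05, follows. The analysis uses an R package for this design, described as fitting a constrained longitudinal model.

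**SAP, Secondary Analysis.** "Secondary outcome measure was change in HAM-D scores", together with HAM-D response, again at p≤0.05.

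**SAP, opening calculation text.** It reproduces a published method: "To analyze these data we use a statistic based on" h, a weighted sum of the drug-minus-placebo differences in response rate in the two phases. This is the only test statistic written out in the SAP.

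**Protocol, Study Summary, Endpoints.** "The efficacy endpoint will be the antidepressant effect of TLT through week 12, as assessed using the QIDS-C scale". It does not say whether this means change or response.

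**Protocol 5.2, Hypothesis 1.** "We anticipate that TLT will decrease QIDS-C and HAM-D 17 total scores in study subjects significantly more than the Sham treatment".

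**Protocol 5.6.** The primary-aim test "will primarily look at QIDS-C and HAM-D 17 total score mean change on TLT" and compares it with the same changes on sham at p≤0.05. Here the 50% QIDS-C criterion only defines sham non-responders for phase 2. The only responder rates reported as an outcome are CGI-Improvement rates, which "will be estimated at week 6 and 12 of the study (no statistics planned").

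**Protocol 5.3 and 3.1.** The power claim (above 80%) rests on the ELATED-2 effect. Section 3.1 reports that effect as a mean change in HAM-D-17.

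**The concern.** Two things are unsettled. Within the SAP, two outcomes have equal standing and nothing says what pattern of results counts as a positive primary finding. Between the documents, the pair of primary tests differs: the SAP adds a response test that the protocol does not plan, and it places HAM-D, which the protocol's primary-aim text puts beside QIDS-C, among the secondary outcomes. Neither document acknowledges the difference.

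At stake is the meaning of the 5% level. It applies to each test, but the error rate of a claim that the treatment works depends on the missing rule. Without that rule, several different results could each be presented as primary success: QIDS change alone, QIDS response alone, both together, or the protocol's pair.

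**Working it through.** **1. Primary outcomes side by side**

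| Place | QIDS change | QIDS response | HAM-D-17 change |
|---|---|---|---|
| Protocol, Endpoints | QIDS-C named, form not stated | form not stated | not named |
| Protocol 5.2, Hypothesis 1 | yes | no | yes |
| Protocol 5.6 | yes, tested | not tested | yes, tested |
| SAP, Primary Analysis | yes | yes | no |
| SAP, Secondary Analysis | no | no | yes (change and response) |

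QIDS change is the only outcome common to protocol 5.2, protocol 5.6 and the SAP's primary analysis, and it is consistent with the Endpoints text.

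**2. The plan's own figure**

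Protocol 5.3 claims more than 80% power with 21 sham and 12 active observations pooled over phases. It does not say which ELATED-2 effect or which sidedness it used.

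- All subjects: difference 11.7 − 5.3 = 6.4; pooled SD √[(8×7.5² + 8×7.0²)/16] = 7.25; d = 0.88.
- Completers: difference 15.7 − 6.1 = 9.6; pooled SD √[(5×4.4² + 6×7.9²)/11] = 6.55; d = 1.47.
- Normal approximation: power = Φ(d/√(1/21 + 1/12) − z), where √(1/21 + 1/12) = 0.362.
- Two-sided 0.05: 98.2% for completers, 68.4% for all subjects. One-sided, all subjects: 78.6%.

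The claim is therefore met with the completer effect and not with the all-subjects effect. For this point, what matters is that both effects are mean changes on HAM-D-17. The documents give no effect size for QIDS change or for QIDS response. The point does not depend on the power figure.

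**3. Error rate under each possible rule**

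Inputs: two-sided 0.05 for each test, so c = 1.96 (p≤0.05 is the SAP's; two-sided is my assumption, because neither the SAP's primary analysis nor protocol 5.6 states sidedness). The correlation r between the two QIDS test statistics is not in the documents, so a range is assumed. With Z1 and Z2 standard normal and correlated r:

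- Either suffices: 1 − P(|Z1| ≤ c and |Z2| ≤ c).
- Both required, both nulls true: 0.05 + 0.05 − (either).

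| r | Either suffices | Both required, both nulls true |
|---|---|---|
| 0 | 9.75% | 0.25% |
| 0.5 | 9.07% | 0.93% |
| 0.7 | 8.35% | 1.65% |
| 0.8 | 7.81% | 2.19% |
| 0.9 | 7.04% | 2.96% |

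If both are required and only one null is true, a false claim needs rejection of that true null, so its probability is at most 5%.

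**4. How plausible is the range of r?**

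Null simulations of the two-phase design used 24% dropout before week 6 (protocol 5.3), equal phase weights (5.6) and six assumed QIDS scenarios. They gave correlations of 0.51 to 0.69, with 8.3% to 9.1% (either) and 0.9% to 1.7% (both). Critical values were set so that each test rejected 5%, and simple pooled-variance statistics stood in for the SAP's model and for h. These runs therefore inform the correlation only.

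**5. Does each test hold 5%?**

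This is not assured. I simulated h over an unpooled standard error against 1.96, with 8 active and 16 sham subjects, 24% dropout, equal weights and assumed null response rates of 20–40% (phase 1) and 10–30% (phase 2), in 20,000 trials per setting. It rejected in about 10% to 12% of trials. The figures in step 3 are thus idealised.

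**The case against.** The strongest reply is that no inflation has been shown. The SAP never says that either outcome suffices. If both must be significant, each test may properly stay at 0.05, and the only cost is power. This stands: the defect is the missing rule, and the inflation is conditional on one way of filling it.

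A reader might infer that the trial runs at a false-positive rate of about 9%. The documents do not support that. The figure needs the either-suffices rule, an assumed correlation and tests that hold exactly 5%. A reader might also infer that requiring both always keeps the error well below 5%. That is true only when both nulls are true; with one true, it can reach 5%.

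Other replies have partial force:

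- The SAP does settle HAM-D as secondary, in line with the protocol's Endpoints text. But protocol 5.2 and 5.6 still say otherwise, neither document states that the SAP prevails, and the ambiguity within the SAP would remain.
- The response statistic is a quoted general method, and the SAP names a longitudinal model separately, so score change is not left without a method. This is correct. What is missing is which outcome the quoted statistic serves.
- QIDS response is not foreign to the protocol, which uses the 50% criterion to define non-response. But it is not a tested outcome there.
- Response dichotomises the same scale, so the tests overlap. Even at a correlation of 0.9, the either-suffices rate is 7.0%.

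**Conclusion.** The point holds in this form: the SAP's two main outcomes have no decision rule, and the protocol and SAP define different primary tests. Both are plain on the text, and no other section resolves them.

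The size depends on the rule. If either outcome suffices, the error per Part is about 9.1% to 7.0% for r from 0.5 to 0.9, on the idealised assumption in step 3. If both are required, it is 0.9% to 3.0% with both nulls true and at most 5% with one true.

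It would be tempting to add that the sample-size basis singles out QIDS change. It does not. The ELATED-2 effect is a HAM-D-17 mean change, which favours a score change over a response rate but does not favour QIDS over HAM-D-17. The case for QIDS-C rests on its being common to protocol 5.2, protocol 5.6 and the SAP, and consistent with the Endpoints text.

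The change should be made, but the stakes are limited. Protocol 5.1 describes a feasibility study of 50 subjects, although both documents still test at p≤0.05.

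**What to change.** Before unblinding:

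- Name QIDS-C total-score change as the single primary outcome for each Part, at two-sided 0.05.
- List QIDS response, HAM-D-17 change and HAM-D-17 response as secondary, in the same words in protocol 5.2, protocol 5.6 and the SAP.
- State in the SAP that the quoted response-rate statistic serves the secondary response analysis.

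The cost is wording in three places, with no added subjects or visits and no planned analysis lost. The downside is that a significant response or HAM-D-17 result alone could no longer be reported as a primary success.

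This change settles which outcome is primary. It does not by itself settle which analysis is primary: protocol 5.6 plans both completer and intent-to-treat analyses without ranking them, and describes a t-test with equal phase weights, where the SAP names a longitudinal model and quotes a power-maximising weight. The same edit should fix those choices.
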